4 STATISTICAL/ANALYTICAL ISSUES

4.1 Adjustments for covariates

Not applicable.

4.2 Handling of dropouts or missing data

There will be no imputation of missing data unless otherwise stated in the sections below.

4.2.1 Pharmacokinetics and pharmacodynamics

The reporting and handling of missing values and values that are BLQ in the TFLs is described in [Section 3.1](#). Zero values will be assumed at the predose timepoint on Day 1 of Cycle 1.

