- Mean (arithmetic and geometric), standard deviation, median and quartiles will use 1 decimal place more, or 1 significant figure more – depending on the reporting format of the original data – than the original data. Original data may be data as reported directly onto the eCRF or summary data based on data reported onto the eCRF (e.g. mean of triplicates or percentage change from Baseline);
- Confidence intervals will be presented to the same number of decimal places as the value around which the confidence interval is constructed;
- Minimum and maximum will be reported using the same number of decimal places or significant figures as the original value;
- A minimum of 3 values are required to calculate summary statistics. If only 2 values are available, then these should be presented as the minimum and maximum with other summary statistics reported as missing (" - ");
- If no participants have data at a given timepoint, then only n=0 will be presented;
- Percentage change from Baseline values will be calculated and displayed to 1 decimal place in the listings. In the summaries, where applicable, the arithmetic mean, standard deviation and median percentage change from Baseline values will be presented to 2 decimal places and the minimum and maximum values presented to 1 decimal place.

[figure not shown]
When reporting individual UCB6114 concentration data in listings and figures, and presenting summary statistics in tables, the following rules will apply:

- UCB6114 concentration data should be reported in the listings to the same level of precision as received from the bioanalytical laboratory;
- Missing data should be reported as 'NV' (no value) in the listings;
- Concentrations below the lower limit of quantification (LLOQ) should be reported as BLQ (below the limit of quantification) in the listings;

- BLQ values prior to C_{max} should be set to 0 for purposes of plotting a figure (to capture lag-time);
- Actual sampling times will be used in the spaghetti plots of individual PK concentrations over time, and nominal sampling times will be used in the summaries of geoMean concentrations over time;
- UCB6114 concentration data should be plotted on both linear and semi-logarithmic scales;
- To calculate summary statistics, BLQ values should be set to half the LLOQ value and missing values should be excluded;

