3.3 Definition of Baseline values

Baseline in Part A will be the last available value prior to the first dose of study treatment. Both scheduled and unscheduled values, as well as any repeated values, should be used when defining Baseline.

Measurement-specific Baseline definitions are presented in Table 3-1.

Table 3-1: Definition of Baseline

Measurement	Definition of Baseline
Echocardiogram (LVEF) PD biomarkers from tissue (optional tumor biopsies) Tumor assessments (antitumor activity)	Screening value
12-lead ECG Physical examination and weight Vital signs Clinical laboratory data ECOG performance status	Predose value obtained on Cycle 1, Day 1, or, if missing, Screening value
Serum and urinary markers of bone turnover Circulating Gremlin-1 (cGremlin-1) Immunogenicity (ADA)	Predose sample value obtained on Cycle 1, Day 1

ADA=anti-drug (UCB6114) antibody; ECG=electrocardiogram; ECOG=Eastern Cooperative Oncology Group; LVEF=left ventricular ejection fraction; PD=pharmacodynamic.

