9.2 Pharmacodynamics

The following exploratory PD and biomarker endpoints will be obtained from blood and urine samples which will be analyzed at a number of external laboratory vendors:

- Serum markers of bone turnover;
- Urinary markers of bone turnover;
- cGremlin-1;
- Serum protein/proteomic analysis;
- Transcriptomic analysis;
- Genetic analysis;
- CtDNA.

The impact of UCB6114 on bone turnover will be explored using the serum and urinary markers provided by the analytical laboratory. These markers will be listed for the SS and summarized descriptively over time for the PDS by dose level (treatment group), as described for the clinical laboratory parameters in Section 8.3. For each marker of bone turnover, the mean (\pm standard deviation) value and the mean (\pm standard deviation) change from Baseline value will be plotted over scheduled visit with treatment group overlaid on the same plot.

cGremlin-1 will be reported as concentration in blood by nominal (scheduled) assessment and dose level. Concentrations of cGremlin-1 will be listed for the SS and summarized for the PDS

using descriptive statistics by dose level (treatment group) and nominal (scheduled) sampling timepoints (n, arithmetic mean, standard deviation, median, minimum, maximum, geoMean, geoCV and 95% CI for the geoMean [assuming lognormally distributed data]). Changes from Baseline will also be summarized. Individual study participant cGremlin-1 concentration-time profiles will be displayed graphically in spaghetti plots and geoMean cGremlin-1 concentration and 95% CI will be plotted at each nominal (scheduled) timepoint with treatment group overlaid on the same plot.

Serum protein/proteomic analysis, transcriptomic analysis, genetic analysis and the analysis of the test results from the blood samples taken for ctDNA will be performed and reported separately outside of the CSR.

Hematoxylin and eosin (H & E) staining and immunohistochemistry (IHC) will be used to analyze any available historical tissue biopsy samples obtained prior to a participant's entry into the study (e.g. at the time of diagnosis).

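### The zero assumed at Cycle 1 Day 1 predose is not limited to UCB6114, so it also reaches the Baseline of cGremlin-1 and, in Part A, the bone turnover markers

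*SAP*

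**What the plan says.** Both SAPs open their missing-data rules in Section 4.2 with a general prohibition: "There will be no imputation of missing data unless otherwise stated in the sections below". The section on pharmacokinetics and pharmacodynamics (4.2.1 in Part A, 4.3 in Part A1) then refers to Section 3.1 for missing and BLQ values and adds: "Zero values will be assumed at the predose timepoint on Day 1 of Cycle 1". It does not say which analyte is meant, or whether the zero applies to missing values, BLQ values or all values.

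Table 3-1 in Section 3.3 defines Baseline by measurement. For cGremlin-1 in both parts, and for serum and urinary bone turnover markers in Part A, it is "Predose sample value obtained on Cycle 1, Day 1". The row for laboratory data, vital signs and ECG falls back on Screening when the predose value is missing. The PD row has no such fallback.

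Section 9.2 of both SAPs asks for cGremlin-1 statistics by nominal timepoint, ending with "geoCV and 95% CI for the geoMean [assuming lognormally distributed data]). Changes from Baseline will also be summarized". In Part A it also asks for plots of mean change from Baseline in each bone marker.

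Section 3.1, in its rules for UCB6114 concentration, says: "To calculate summary statistics, BLQ values should be set to half the LLOQ value and missing values should be excluded".

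**The concern.** Before the first dose there is no UCB6114 in the participant, so zero is a natural value for drug concentration. cGremlin-1 and the bone markers are different: they are sampled before dosing precisely so that each participant has a Baseline of their own. A zero in that position is a false Baseline, and the change calculated from it is simply the post-dose value. For that participant a fall in the marker cannot appear, because the change can never be negative.

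The sentence is also a stated exception to the no-imputation rule, so a programmer working from the SAP has a reason to apply it to PD data. Cohorts are small (3 to 6 evaluable participants in Part A, up to 8 in Part A1), so one false Baseline can move a cohort mean a long way. These markers carry the blood and urine PD change-from-Baseline results that the SAPs report in the CSR.

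**Working it through.** The plan states no figure that depends on this rule, so there is nothing to reproduce. The effect follows from algebra. The documents give no marker levels and no rate of missing Baselines, so the values below are assumptions for illustration.

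**Inputs.** Cohort size n: 3 and 6 (Part A SAP, Section 2.3) and 8 (Part A1 SAP, Section 2.3). Assumed true Baseline B = 100 and post-dose value P = 90 or 50, the same for every participant. k is the number of participants whose Baseline is set to zero.

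**Formula.** Change = P - Baseline; with Baseline = 0, change = P. Hence

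- mean change = [(n - k)(P - B) + kP]/n = (P - B) + kB/n
- bias = kB/n

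**Missing-data reading, one zero-filled Baseline (k = 1).**

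| P | n | True mean change | Mean change as analysed |
|---|---|---|---|
| 90 | 3 | -10 | (2 × -10 + 90)/3 = +23.33 |
| 90 | 6 | -10 | (5 × -10 + 90)/6 = +6.67 |
| 90 | 8 | -10 | (7 × -10 + 90)/8 = +2.50 |
| 50 | 3 | -50 | (2 × -50 + 50)/3 = -16.67 |
| 50 | 6 | -50 | (5 × -50 + 50)/6 = -33.33 |

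A true fall is reported as a rise when kB/n exceeds B - P, that is, when the proportional fall (B - P)/B is smaller than k/n. For one zero-filled Baseline the limit is 1/3 = 33.3% at n=3, 1/6 = 16.7% at n=6 and 1/8 = 12.5% at n=8. Larger falls keep their sign but are understated. With k = 0 the bias is 0.

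**Literal reading (k = n).** Mean change = P. With P = 90 it is 90, the raw post-dose mean, whatever the Baseline was.

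**Geometric statistics.** The cGremlin-1 geometric mean and geometric CV are taken on the log scale, and log(0) does not exist. One zero at the Baseline timepoint leaves both undefined there.

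**Against Section 3.1.**

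- Missing predose value: excluded under 3.1, zero under 4.2.1/4.3.
- BLQ predose value in a summary: half the LLOQ under 3.1, zero under 4.2.1/4.3. For a BLQ Baseline the two differ by only half the LLOQ per participant, so the large bias comes from zero-filling missing values.
- BLQ before Cmax on a plot: already zero under 3.1, so the extra sentence is not needed for that purpose.

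**The case against.** A reader might infer that every PD change from Baseline in the study becomes the raw post-dose value. The documents do not support that. The rule follows a section on missing data, and Table 3-1 refers to a sample that was obtained, so a measured Baseline would most naturally stand. The universal effect needs the most literal reading, and even then it reaches only the blood and urine markers. Tissue markers use the Screening value as Baseline and cannot be affected.

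Context also suggests that drug concentration was meant. The sentence just before refers to Section 3.1, whose visible rules are written for UCB6114 concentration. This makes the intention plausible, but the section heading and the wording still include PD.

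For bone markers, Section 9.2 points to the laboratory summaries in Section 8.3, and those take their BLQ handling from 4.2.2. That may spare a BLQ bone-marker Baseline. Section 4.2.2 says nothing about missing values, so a missing one is still exposed.

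Section 3.3 also lets unscheduled and repeat predose values serve as Baseline. This should make missing Baselines rarer, but it does not settle what happens when one is missing.

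Two further inferences should not be drawn:

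- **Loss of the UCB6114 predose geometric mean.** This is largely moot. Section 3.1 reports only minimum and maximum once BLQ plus missing values exceed one third, which is to be expected before the first dose.
- **Concealment of a sampling or dosing error.** Concentrations are listed as received from the laboratory with actual and nominal times, and out-of-window samples go to the data evaluation meeting, so a measured predose value would remain visible.

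**Conclusion.** The rule is misstated in both SAPs and should be corrected. On the narrow reading, each zero-filled Baseline shifts the cohort mean change by B/n, which can reverse its sign in cohorts of this size, and it leaves the cGremlin-1 Baseline geometric mean and geometric CV undefined. On the literal reading, the changes in cGremlin-1 and, in Part A, the bone markers would all equal the post-dose values. Either way the sentence disagrees with Section 3.1.

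The actual size cannot be stated: it depends on marker levels and on how many predose samples are missing, and the documents give neither. If none is missing or BLQ and the narrow reading is used, there is no effect. The consequence is confined to descriptive, exploratory blood and urine PD outputs. The primary safety endpoints and the tissue PD markers are not affected. The use of the zero in NCA cannot be fully judged, because part of the PK material is redacted.

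**What to change.** In Part A SAP 4.2.1 and Part A1 SAP 4.3:

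- Limit the zero assumption to UCB6114 concentration, for NCA and plots.
- State that summary tables follow Section 3.1 (missing excluded, BLQ at half the LLOQ).
- State that the zero does not apply to PD markers, and that a missing PD Baseline leaves change from Baseline missing.

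The cost is a sentence or two in each SAP and a check that the PD analysis datasets contain no imputed zero at Baseline. If the sponsor always meant drug concentration only, no planned result changes.

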4.2.2 Safety laboratory data

The rules for handling values that are BLQ in the safety laboratory data will be the same as those described for PK data in [Section 3.1](#). Any values above the limit of quantification (ALQ) will be assigned as the value of upper limit of quantification.

4.2.3 Dates and times

Partial dates may be imputed for the following reasons:

- Classification of adverse events (AEs) as treatment-emergent;
- Classification of medications recorded on the concomitant medications log as prior or concomitant;
- Calculation of time since initial diagnosis, time since completion of most recent line of prior anti-cancer systemic therapy and time since progression/relapse on most recent line of prior anti-cancer systemic therapy.

Imputed dates will not be shown in the listings; all dates will be displayed as reported in the database.

The following rules will be applied for partial onset/start dates:

- If only the month and year are specified and the month and year of the first dose of study treatment is not the same as the month and year of the start date then the 1st of the month will be used, or the date of the Screening visit if this is later (if the latter imputation results in an end date that is earlier than the start date, then the 1st of the month will be used);
- If only the month and year are specified and the month and year of the first dose of study treatment is the same as the month and year of the start date, then the date of the first dose of study treatment will be used. If this results in an imputed start date that is after the specified end date, then the 1st of the month will be used, or the date of Screening if this is later (if the latter imputation results in an end date that is earlier than the start date, then the 1st of the month will be used). If the imputed date is the same date as the date of the first dose of study treatment then, for AEs, the event will be regarded as treatment-emergent. For medications, the medication will be classified as concomitant;
- If only the year is specified, and the year of the first dose of study treatment is not the same as the year of the start date then January 01 will be used;
- If only the year is specified, and the year of the first dose of study treatment is the same as the year of the start date, then the date of the first dose of study treatment will be used. If this results in an imputed start date that is after the specified end date, then January 01, or the date of the Screening visit if this is later will be used (if the latter imputation results in an end date that is earlier than the start date, then January 01 will be used). If the imputed date is the date of the first dose of study treatment then, for AEs, the event will

be regarded as treatment-emergent. For medications, the medication will be classified as concomitant.

- If the onset/start date is completely missing then the onset/start date will be imputed to the date of first dose of study treatment and therefore, for AEs, the event will be regarded as treatment-emergent and, for medications, the medication will be classified as concomitant.

The following rules will be applied to partial end/stop dates:

- If only the month and year are specified, then the last day of the month will be used;
- If only the year is specified, then December 31 of the known year will be used;
- If the stop date is completely unknown, the stop date will not be imputed.

Note that the start date or stop date of a prior medication (partial or otherwise) should not be imputed past the Screening date - 1.

In addition to onset and stop dates, the onset and end times of AEs occurring on the day of infusion will be collected on the eCRF. Onset and end times may also be recorded for other AEs that do not occur on the same day as the infusion. The duration of AEs with onset and end times will be calculated in days and hours:minutes (hh:mm) as:

$$\text{Duration of AE} = \text{End Date and Time} - \text{Onset date and time}$$

In cases where only the onset and stop dates are recorded for an AE, the duration of an AE will be calculated in days as:

$$\text{Duration of AE} = (\text{Stop Date} - \text{Onset Date}) + 1$$

Note that for participants who have an AE which starts and stops on the same day, but with only a start time or only a stop time recorded, it will be assumed that their AE started from 00:00 (if no start time is recorded) and ended at 23:59 (if no stop time is recorded) on that day.

If the date of a participant's initial diagnosis is incomplete, it will be imputed to the most recent feasible date for the calculation of time since initial diagnosis as follows:

- If only the day is missing, it will be imputed to the last day of the known month;
- If the day and month are missing, it will be imputed to December 31 in the known year;
- If the date of initial diagnosis is completely missing, then time since initial diagnosis will not be calculated.

The above date imputation rules will be applied to partially missing stop dates of a participant's last prior anti-cancer systemic therapy as well as partially and completely missing dates of progression/relapse on last prior anti-cancer systemic therapy.

In cases where the stop date of a participant's last prior anti-cancer systemic therapy and/or a participant's date of progression on last line of prior anti-cancer systemic therapy is completely missing, the participant's Screening date - 1 will be used in the calculation of the time since completion of most recent line of prior anti-cancer systemic therapy and the time since progression/relapse on most recent line of prior anti-cancer systemic therapy, respectively.

Note that partial dates will not be imputed as a participant's first dose of study treatment in the calculation of time since initial diagnosis, time since completion of most recent line of prior anti-cancer systemic therapy and time since progression/relapse on most recent line of prior anti-cancer systemic therapy.

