- Best response to the most recent prior anti-cancer therapy regimen
- Number of prior anti-cancer systemic therapy + radiotherapy regimens (0, 1, 2, 3, >3)
- Best response to the most recent anti-cancer systemic therapy + radiotherapy regimen
- Reasons for discontinuation of the most recent line^[a]
- Time from completion of most recent line^[a] to the start of study treatment (<1 month, 1-<3 months, 3-6 months, >6 months)^[b]
- For participants that progressed after their most recent line^[a], the time from progression to the start of study treatment (<1 month, 1-<3 months, 3-6 months, >6 months)^[b]
- Number of prior anti-cancer radiotherapies (including radiotherapies given alone and concurrently with anti-cancer systemic therapy) (0, 1, 2, >2)
- Number of prior anti-cancer surgeries and procedures (0, 1, 2, >2)

^[a] Most recent line is the last prior anti-cancer therapy regimen received which may be a prior anti-cancer systemic therapy given alone or concurrently with radiotherapy.

^[b] 1 month = 30 days.

Time from completion and time from progression relative to the last line of anti-cancer systemic therapy will also be summarized using frequency counts and percentages as well as summary statistics.

The number and percentage of participants with any prior anti-cancer systemic therapy, and any prior anti-cancer systemic therapy given concurrently with radiotherapy will be summarized for the SS by treatment group and for all participants, and by WHODD Anatomical Main Group [Level 1 term text], Pharmacological Subgroup [Level 3 term text] and PT.

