6.6 Prior and concomitant medications

Prior medications will include any medications that started prior to the date of the first dose of study treatment. This will include medications that started prior to the first dose and continued after.

Concomitant medications will include medications with a start date on or after the first dose of study treatment and prior to the date of the last dose of study treatment + 30 days, and whose stop date is either missing, or on or after the date of the first dose of study treatment. Any medications with a start date prior to the first dose of study treatment and a stop date after, or continued to be ongoing during the study, will also be classified as concomitant medications. Medications with a start date > 30 days after the last dose of study treatment will be considered as post-study medications and will not be included in the summaries of concomitant medication.

Any medication that started prior to, and stopped after the first dose of study treatment, or continued to be ongoing during the study, will be classified as both prior and concomitant.

Any medications with missing start dates will be classified as both prior and concomitant provided that a stop date is not present or a stop date is present and it is prior to the first dose of UCB6114.

Any medications with partially missing dates will be handled as described in [Section 4.2.3](#) to classify them as prior or concomitant.

All medications (prior, concomitant and post-study) will be listed for the ES. Any prohibited concomitant medications, rescue medications or steroid use will be identified via a medical review and flagged in this listing.

Prior and concomitant medications (per the definitions above) will be summarized for the SS by treatment group and by WHO-DD Anatomical Main Group [Level 1 term text], Pharmacological Subgroup [Level 3 term text] and PT. The reported term will be included in the listing. Separate summaries will be presented for prior medications and concomitant medications. As per the definitions above, prior medications which continued into the Treatment Period will also be classified as concomitant and will be included in both summaries.

All tabulations will be sorted alphabetically by Level 1 term, alphabetical Level 3 term within Level 1 and decreasing frequency of PT in all study participants.

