- If only the year is specified, and the year of the first dose of UCB6114 is the same as the year of the start date, then the date of the first dose of UCB6114 will be used. If this results in an imputed start date that is after the specified end date, then January 01, or the date of the Screening visit if this is later will be used (if the latter imputation results in an end date that is earlier than the start date, then January 01 will be used). If the imputed date is the date of the first dose of UCB6114 then, for AEs, the event will be regarded as treatment-emergent. For medications, the medication will be classified as concomitant.
- If the onset/start date is completely missing then the onset/start date will be imputed to the date of first dose of UCB6114 and therefore, for AEs, the event will be regarded as

treatment-emergent and, for medications, the medication will be classified as concomitant.

The following rules will be applied to partial end/stop dates:

- If only the month and year are specified, then the last day of the month will be used;
- If only the year is specified, then December 31 of the known year will be used;
- If the stop date is completely unknown, the stop date will not be imputed.

Note that the start date or stop date of a prior medication (partial or otherwise) should not be imputed past the Screening visit date - 1.

In addition to onset and stop dates, the onset and end times of AEs occurring on the day of UCB6114 infusion will be collected on the eCRF. Onset and end times may also be recorded for other AEs that do not occur on the same day as the UCB6114 infusion. The duration of AEs with onset and end times will be calculated in days and hours:minutes (hh:mm) as:

$$\text{Duration of AE} = \text{End Date and Time} - \text{Onset Date and Time}$$

In cases where only the onset and stop dates are recorded for an AE, the duration of an AE will be calculated in days as:

$$\text{Duration of AE} = (\text{Stop Date} - \text{Onset Date}) + 1$$

Note that for participants who have an AE which starts and stops on the same day, but with only a start time or only a stop time recorded, it will be assumed that their AE started from 00:00 (if no start time is recorded) and ended at 23:59 (if no stop time is recorded) on that day.

If the date of a participant's initial diagnosis is incomplete, it will be imputed to the most recent feasible date for the calculation of time since initial diagnosis as follows:

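### In both SAPs the Screening minus 1 cap drops some continuing medications with partial stop dates from the concomitant summary; wholly missing progression dates have two conflicting rules, one forcing the under-1-month category

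*SAP*

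**What the plan says.** **Medications.** The Part A SAP, Section 4.2.3, sets a partial stop date to the end of the recorded month, or to 31 December if only the year is known, and leaves a wholly unknown stop date alone. It then adds that "the start date or stop date of a prior medication (partial or otherwise) should not be imputed past the Screening date - 1". The Part A1 SAP, Section 4.4.1, has the same general rules and the same cap: "the start date or stop date of a prior medication (partial or otherwise) should not be imputed past the Screening visit date - 1".

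Section 6.6 defines prior medications as those started before first dose and adds: "This will include medications that started prior to the first dose and continued after". It also says: "Any medication that started prior to, and stopped after the first dose of study treatment, or continued to be ongoing during the study, will be" counted as both prior and concomitant. Section 6.6 sends partial dates back to the date section for this classification. The Part A1 SAP has the equivalent text.

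**Last prior anti-cancer therapy.** For initial diagnosis, Section 4.2.3 imputes partial dates to the end of the month or year and calculates no interval if the date is wholly missing. It extends those rules to partially missing therapy stop dates and to "partially and completely missing dates of progression/relapse on last prior anti-cancer systemic therapy". The next paragraph deals with a therapy stop date or progression date that is wholly missing. It says: "Screening date - 1 will be used in the calculation of the time since completion of most recent line of prior anti-cancer systemic therapy"; the same substitution serves for time since progression. Section 6.3 tabulates both intervals, to the start of study treatment, as "<1 month, 1-<3 months, 3-6 months, >6 months", with a month of 30 days. The Part A1 SAP repeats all of this.

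**The concern.** The cap makes sense for a medication that ended before the participant entered screening. As worded, it covers every prior medication, and Section 6.6 puts continuing medications in that class. Applied literally, it can replace a stop known to fall during treatment with one before Screening, so that a medication taken on study is missing from the concomitant table.

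The second issue is partly a contradiction and partly a choice of value. A programmer cannot both leave the interval uncalculated and compute it from Screening minus 1. If the second rule is followed, an unknown history is reported as the most recent progression, or the shortest washout, that the table can show. These tables describe the population entered, in cohorts of 3 to 6 (Part A) or up to 8 (Part A1).

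Section 4.2.3 keeps imputed dates out of the listings. A reader would see a missing or partial date listed and a definite category tabulated, with nothing linking the two.

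**Working it through.** The plan gives no figure of its own here, so the check applies the stated rules to dates.

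**1. The cap on medications.** Assumed dates: Screening 20 Jan 2022, first dose 10 Feb 2022 (21 days later), cap = 19 Jan 2022 (22 days before first dose). A medication started before first dose is concomitant if its stop is after first dose or it is ongoing. The capped stop is the earlier of the general-rule stop and the cap.

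| Start | Recorded stop | General rule | Concomitant? | With cap | Concomitant? |
|---|---|---|---|---|---|
| 5 Nov 2021 | Mar 2022 | 31 Mar 2022 | yes | 19 Jan 2022 | no |
| 5 Nov 2021 | Feb 2022 | 28 Feb 2022 | yes | 19 Jan 2022 | no |
| 5 Nov 2021 | 2022 | 31 Dec 2022 | yes | 19 Jan 2022 | no |
| 5 Nov 2021 | Jan 2022 | 31 Jan 2022 | no | 19 Jan 2022 | no |
| 1 Feb 2022 | Mar 2022 | 31 Mar 2022 | yes | 19 Jan 2022 | no |

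- Rows 1, 2 and 5: the capped stop lies outside the recorded month.
- Row 3: it stays inside the recorded year but reverses the year-end rule. It would leave the year if Screening fell in the year before; Screening on 20 Dec 2021 with a recorded stop year of 2022 gives 19 Dec 2021.
- Row 4: no change in classification.
- Row 5: the stop precedes the medication's own start. The start-date rules guard against reversed dates; the cap has no such guard.
- A complete recorded stop date is not imputed, and a wholly unknown one is left unimputed, so neither moves.

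**2. Wholly missing progression or relapse date.** Under the diagnosis-date rules, the interval is not calculated. If the cross-reference were instead read as the general stop-date rules, a wholly unknown date is not imputed, so again there is no interval. The following paragraph supplies Screening minus 1. The two instructions are incompatible on either reading.

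**3. What Screening minus 1 produces.** Let k be the days from Screening to first dose; Section 3.2.2 allows up to 28.

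Interval = first dose − (Screening − 1) = k + 1

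| k | 1 | 7 | 14 | 21 | 28 |
|---|---|---|---|---|---|
| Interval (days) | 2 | 8 | 15 | 22 | 29 |

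The maximum is 29, below the 30-day month. The interval reaches 30 only if Screening is out of window (k = 29 or more), or at exactly k = 28 if the count adds a day. The SAPs state no added day for this interval.

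**4. Weight of one participant in the shortest category.** 1/6 = 16.7% to 1/3 = 33.3% in a cohort of 3 to 6; 1/8 = 12.5% in a cohort of 8.

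**The case against.** The best defence is that the cap was meant for medications that are prior only, and that a sensible programmer would read it so. A stop recorded as March with first dose on 10 February already shows overlap, and Section 6.6 classes such a medication as both prior and concomitant without any imputed day. That is the likely intent. It is not what the text says: the cap has no exception for continuing medications, and Section 6.6 sends partial dates to the section containing it. The real ambiguity, where the stop month or year contains first dose, cannot be settled without an imputation rule.

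Several stronger readings should be resisted.

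- A reader might infer that the cap ends all continuing medications. It does not; only partial stop dates on medications started before first dose move.
- A reader might infer that steroids or prohibited agents would go undetected. Section 6.6 lists every medication and flags these by medical review. Section 3.4 makes prohibited medication a category of important protocol deviation, and Section 10.1.1 identifies anti-cancer therapy for PFS censoring by medical review and the survival follow-up pages. None of this rests on the imputed stop.
- A reader might infer that every missing last-therapy date becomes a short washout, or that the therapy-stop substitution contradicts the plan. Partially missing dates go to the end of the month or year. For therapy stops, the diagnosis-date rules are extended only to partial dates, so Screening minus 1 is a specific exception. It also resembles the most-recent-feasible principle used for diagnosis. The objection there is to the forced result, not to consistency.
- A reader might infer that time since relapse in Section 6.4 becomes 1 day. It would if the same imputed date were used, since Screening − (Screening − 1) = 1, but the substitution rule does not cite that section.
- The percentages above are the weight of any one participant. They do not estimate an effect, because nothing in the documents shows how often these dates are wholly missing.

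**Conclusion.** The concern stands in a limited form, in both SAPs. The cap conflicts with the definition of prior medication and with the general stop-date rules. It wrongly removes from the concomitant summary a medication started before first dose whose partial stop date falls during treatment. Wholly missing progression or relapse dates have two incompatible rules. The Screening minus 1 substitution, for these and for wholly missing therapy stops, fixes the category at under 1 month whatever the true interval.

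The 29-day ceiling assumes Screening within 28 days and a plain date difference. The consequence is confined to descriptive medication and prior-therapy tables; no effect on the primary safety endpoints is shown. The number of records affected is unknown. The text is worth correcting before database lock, because otherwise the conflict will be settled silently in programming.

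**What to change.** Make the same changes in Section 4.2.3 of the Part A SAP and Section 4.4.1 of the Part A1 SAP.

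1. Restrict the cap to prior anti-cancer therapy records, or to medications known to have ended before Screening.
2. State that no stop date is imputed outside its recorded month or year, or before the medication's start date. Other partial stop dates then follow the existing month-end and year-end rules, so a possible overlap counts as concomitant.
3. For a wholly missing progression or relapse date, report Missing and calculate no interval, as for initial diagnosis, and remove the Screening minus 1 substitution. Merely dropping wholly missing dates from the cross-reference would end the contradiction but keep the forced category.
4. Preferably treat a wholly missing last-therapy stop date the same way.

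The cost is SAP wording and two derivations. A few intervals would be shown as missing, and a few medications would return to the concomitant summary.
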